## 7 STUDY SCHEDULE AND ASSESSMENTS

### 7.1 Screening Procedures and Assessments

All of the assessments required as part of the study are indicated in [Table 7-1](#) organized by visit date, with assessments required indicated with an “X” at the specific visits when they should be performed. Laboratory and radiological assessments performed as part of the parent study and/or standard of care prior to signing the rollover informed consent may be used if performed within the screening time window (21 days for laboratory assessments). No radiologic assessments will be collected as part of the rollover study. Assessments performed as part of the parent study should be included in the parent study database. Please note, if the last dose of IMCgp100 on the parent study and the first dose of IMCgp100 on the rollover study are separated by more than 21 days, the first dose of IMCgp100 must be administered with overnight inpatient monitoring; given the risk of severe infusion-related toxicity and potential for hypotension (refer to [Section 1.4](#) for details of clinical experience with IMCgp100).

During the course of the study visits, test and/or procedures should occur on schedule whenever possible. A visit window of  $\pm 7$  days is allowed unless otherwise indicated in the protocol.

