### 1.4.3 Daily Dosing: Dose Escalation Results

The dose escalation in the daily dosing regimen Phase I arm (Arm 2) is complete with the dosing regimen identified as a flat dose of 50 mcg QDx4 administered every 3 weeks (n=15 patients across 5 dose levels ranging from 10 mcg to 50 mcg). [REDACTED]

For further details refer to the most recent version of the IMCgp100 Investigator's Brochure.

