**Table 2-1 Maximum Dose and Schedule of Administration Based Upon Parent Study**

Study Protocol	Maximum IMCgp100 Dose and Frequency of Administration
IMCgp100-01	50 mcg IV weekly (QW)

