6.4. Windowing Conventions

There will be no post-hoc visit windowing for the analyses performed for this study. All data will be organized and analyzed according to the scheduled visit times (allowing for ± 7 days) as outlined in the Protocol Section 7-1 and by the visit denoted on the eCRF.

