13.1. Study Drug Exposure Derivations

A cycle is defined as 28 days = 4 weeks, and at least 1 dose administration visit per cycle for each of the treatment regimen for IMCgp100 (doses are given every week).

The following will be derived:

- *Number of cycles started* = total number of cycles of study drug received (including partial cycles), during the rollover study
- *Number of cycles completed* = total number of complete cycles of study drug received without any interruption, during the rollover study
- *Total planned dose* = sum of the total dose levels that a patient planned to receive during the rollover study, up to the date of last study drug administration
- *Duration of treatment (days)* = (date of last study drug administration – date of first study drug administration in the rollover study + 1). Note that this calculation does not include any post dose rest period. *Duration of treatment from first parent study dose (days)* = (date of last study drug administration – date of first parent study dose of IMCgp100 + 1). Note that this calculation does not include any post dose rest period
- *Duration of interruption (days)* = (start date of next study drug administration following interruption - date of visit in which interruption started). Note that this is calculated for each interruption a given patient has and is only calculated where study drug administration restarts following interruption.
 - “Date of visit in which interruption started” = ‘date of visit’ from the *Date of Visit* eCRF pages, where the visit may also be a visit classified as “not done”. If it is clear that an interruption to dosing has occurred, but no *Date of Visit* eCRF page nor *Administration of Study Drug* eCRF page is entered at least 14 days (i.e. at least 7 days ± 7 day visit window) following the previous dosing visit, where dosing would have been expected, then the date of the *expected* next dose following last administered dose, may be used instead (=previous ‘start date of study drug administration’ + 14 days). See the definition of a *dose interruption* below.
 - If a patient does not have a “start date of *next* study drug administration following interruption” then a dose interruption is not counted because either:
 - The Date of study drug discontinuation from the *End of Treatment* page of the eCRF is filled out, in which case the study drug was discontinued rather than interrupted, or

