 - The outcome (interruption or discontinued) is unknown at the time of data cut off, where the study drug discontinuation from the *End of Treatment* page is missing and study drug administration remains skipped or omitted. In this case, it is assumed there was no interruption, until there

is evidence of the study drug administration restarting.

- *Total actual dose received* = sum of the total dose levels that a patient received during the rollover study, up to the date of last study drug administration. The same considerations as for *Total planned dose* above apply here.
- Dose intensity (dose per week) = $[\text{Total actual dose received} / \text{Duration of treatment (days)}] \times 7$
- Planned dose intensity (dose per week) = $[\text{Total planned dose} / \text{Duration of treatment (days)}] \times 7$
- Relative dose intensity (%) = $(\text{Dose intensity} / \text{Planned dose intensity}) \times 100$

Additional Notes on Derivations:

- a. The *Administration of Study Drug* eCRF page will be used for these calculations, unless otherwise noted.
- b. The *number of cycles started* is counted for all cycles of dosing in which study drug was actually administered. Any administration of study drug received, regardless of the 'Actual dose administered' on the eCRF (any dose > 0 units), that occurs in a given cycle (as indicated by the visit) will be counted as one cycle of that study drug.
 - a. Note: Multiple doses within a Cycle do not count multiple times towards the *number of cycles*. For example, four doses (> 0 units) of IMCgp100 during visits in Cycle 1 count as one cycle of study drug since all these dose administrations occurred during a single Cycle (i.e. Cycle 1).
- c. The number of cycles completed is counted for all cycles of dosing in which study drug was actually administered, and furthermore where no interruption occurs. Therefore, in a 4-week cycle, all doses each week must be administered for the entirety of the cycle, in order to count. Reduced doses are allowed, as per number of cycles started above.

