- d. The *total planned dose* is based on either the 'Parent Study Dose IMCgp100', or if applicable, the dose entered in 'Was dose changed from parent study' item, on the *Parent Study Details -IMCgp100* eCRF page. This planned dose is summed up over all visits where a patient planned to receive study drug, even if the said dose is actually missed during the visit, up until the cut-off as described above. This calculation is necessary for the planned dose intensity, which is used to calculate the relative dose intensity.
- e. The *total actual dose received* is based on the 'Actual dose administered' entered on the *Administration of Study Drug* eCRF for each visit administration of study drug. The actual dose administered is summed up over all visits where a patient actually received study drug, up until the cut-off as described above.
- f. The date of first study drug administration is taken from the earliest 'Dose start date' entered on the eCRF.
- g. The date of last study drug administration is taken from the latest 'Dose end date'

entered on the eCRF.

Definitions of Dose Interruption:

Dose interruption – an entire dosing visit is skipped or entered as omitted in the eCRF. To clarify, if a dose on a single day is restarted and partial or entire dose is still taken, then this is not a dose interruption. Dose interruptions will be flagged on the *Administration of Study Drug* eCRF page where the response to ‘*Did the patient receive investigational product at this visit?*’ is equal to ‘*No, reason for dose omission*’. Also, dose interruptions are counted in cases where a patient misses an entire study visit, where dosing is expected.

A single interruption is defined as any length of time a patient misses dosing visits. For example, for IMCgp100 which is administered weekly, then a single dose interruption would be defined regardless of whether only 1 week was missed or 2 consecutive weeks dosing were missed.

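### SAP 13.1 starts an undocumented interruption 14 days after the last dose although dosing is weekly; the linked ±7-day visit window equals the dosing interval

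*Protocol*

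**What the plan says.** Protocol Table 2-1 sets the maximum at 50 mcg IV weekly for patients from IMCgp100-01. Table 7-1 places infusions on Days 1, 8, 15 and 22 of a 4-week cycle. Section 7.1 asks for visits on schedule where possible, then says that a window of ±7 "days is allowed unless otherwise indicated in the protocol". Section 7.2.1 refers to Table 7-1 for visit windows, but the visible table and footnotes give none for infusions. Footnote h refers to Section 6.1, which is partly redacted.

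SAP 6.4 repeats the ±7-day allowance. SAP 13.1 carries it into dosing. The duration of an interruption is the date dosing restarts minus the date of the visit at which the interruption began, and that visit may be one recorded as not done. A fallback covers the case where no visit or administration page is entered "at least 14 days (i.e. at least 7 days ± 7 day visit window) following the previous dosing visit". The date of the expected "next dose following last administered dose, may be used instead", and the SAP sets it at the previous administration date plus 14 days.

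The SAP defines a dose interruption as the case where "an entire dosing visit is skipped or entered as omitted in the eCRF". Consecutive missed visits count as one interruption.

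**The concern.** For a weekly drug the next dose is expected 7 days after the last one. The fallback puts it at 14 days because it adds the visit window to the interval. The same dosing history can then receive two different durations, depending only on whether the site entered a page for the missed visit. Dose interruptions are part of the tolerability endpoint in Protocol 4.4, so the derivation should not depend on paperwork.

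The window itself raises a second question. A visit window as wide as the dosing interval lets the windows of adjacent infusions overlap. The protocol names infusion-related hypotension as a risk, and its only visible rule on the gap between doses covers long gaps: more than 21 days before the first rollover dose. No visible text says whether weekly means at least 7 days apart or once per study week.

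**Working it through.** **Inputs.** Dosing interval: 7 days (Tables 2-1, 6-1 and 7-1; SAP 13.1). Window: ±7 days (Protocol 7.1, SAP 6.4). Maximum dose: 50 mcg (Table 2-1). Fallback start of interruption: previous dose + 14 days (SAP 13.1).

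**Step 1: reproduce the SAP figure.** 7-day interval + 7-day window = 14 days, as stated.

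**Step 2: interruption length.** Let P be the day of the last dose and R the day dosing resumes.

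- Fallback: R − (P + 14).
- Visit page for the first missed dose, carrying its nominal date (assumed): R − (P + 7).
- Difference: 7 days, whatever R is.

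| History | Fallback | With a Day 8 page marked as not done | Interruptions counted |
|---|---|---|---|
| Dose Day 1; Days 8 and 15 missed; resume Day 22 | 22 − 15 = 7 days | 22 − 8 = 14 days | 1 |
| Dose Day 1; Day 8 missed; resume Day 15 | 15 − 15 = 0 days | 15 − 8 = 7 days | 1 |

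The second row lies on the edge of the 14-day condition, and the SAP wording does not settle whether the fallback applies there. If it applies, a missed dose has an interruption of zero length. The first row does not have this difficulty.

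**Step 3: expected date at +7.** The fallback becomes R − (P + 7): 14 days and 7 days in the two rows, equal to the visit-page route.

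**Step 4: the visit window.** At ±7 days the Day 8 visit covers Days 1 to 15 and the Day 15 visit covers Days 8 to 22. A Day 8 infusion given on Day 14 and a Day 15 infusion given on time are both in window. The gap is 15 − 14 = 1 day, and the dose is 2 × 50 = 100 mcg in 2 days. Day 14 lies in study week 2 (Days 8–14) and Day 15 in study week 3 (Days 15–21), so a once-per-study-week reading is met. A reading of at least 7 days apart is not.

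**Step 5: would a narrower window be enough?** With ±w days around nominal dates, the gap between adjacent infusions runs from 7 − 2w to 7 + 2w days: 5–9 for w = 1, 3–11 for w = 2 and 1–13 for w = 3. Even ±3 days allows a 1-day gap, so a minimum interval has to be stated as such.

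**The case against.** **On the SAP rule.** It is an optional fallback for missing pages. SAP 13 summarizes the number of interruptions and lists reasons; it does not name duration for summary, and Protocol 9.6.1.4 also refers to the number. This stands and keeps the point minor. One can also argue that +14 is deliberate, because a weekly visit is not overdue until its window closes. That justifies waiting 14 days before deciding that a visit was missed. It does not justify dating the start there, since the visit-page route does not wait for the window to close.

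**On the window.** A reader might infer that the protocol permits bunched infusions. The documents do not support that. Section 7.1 yields to other protocol text, Table 2-1 caps frequency as well as dose, and the redacted part of Section 6.1 may set a minimum gap. The SAP authors, presumably working from the full protocol, still applied ±7 days to dosing visits. A narrower dosing window in Section 6.1 is therefore unlikely, but a minimum gap there cannot be excluded. SAP 13.1 also uses the window only on the late side, to date a missed dose, and authorizes no early infusion.

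A reader might also compress four infusions into Days 1, 8, 14 and 15. That breaks the weekly maximum on either reading: the gaps include 6 days and 1 day, and Days 8 and 14 both fall in study week 2.

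A reader might blame the window for the fact that relative dose intensity does not respond to timing. The cause is elsewhere: the SAP divides actual and planned dose by the same duration, so duration cancels whatever the window is.

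**On safety.** In the parent study's daily arm, "the dosing regimen identified as a flat dose of 50 mcg QDx4 administered every 3 weeks" covers consecutive-day infusions at this dose, although this rollover's visible schedule is weekly only. Laboratory panels before every dose, toxicity holds, and hospitalization for the next 2 doses after grade 3 or 4 hypotension also apply. These make the safety bearing modest.

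**Conclusion.** The SAP's +14-day rule is wrong as written for a weekly drug, and this does not depend on redacted text. It shortens a derived interruption by 7 days relative to a documented one, assuming that the last dose was on its nominal day and that the page carries the nominal date of the missed visit. It leaves the interruption count unchanged. No effect on the primary endpoint, the incidence of adverse events, is shown.

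The protocol point is an ambiguity, not a contradiction. The Days 14 and 15 case holds only if weekly means once per study week and Section 6.1 sets no minimum gap. Together the two points are minor.

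**What to change.** **SAP 13.1.** Define the expected next dose as the previous dose + 7 days. The 14-day wait can stay as the test for recognizing an undocumented missed visit, with wording that settles the case of resumption on exactly day 14 after the last dose. Say that the rule will be used, not that it may be. The cost is a small SAP wording change and one programming constant.

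**Protocol.** Unless the redacted part of Section 6.1 already does so (in which case cross-reference it), state in Section 7.1 and a Table 7-1 footnote that:

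- the ±7-day window does not override the weekly maximum;
- infusions are separated by a stated minimum interval;
- a dose that cannot meet that interval is omitted and not made up.

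The interval is a clinical choice for the sponsor, since the visible documents give no basis for a value. For illustration only, 5 days is the shortest gap that a ±1-day window on nominal dates would allow, and 3 days the shortest for ±2. SAP 6.4 should then refer to the infusion rule.

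This part needs an amendment with IRB or IEC approval, as Amendment 2 did, and can wait for the next one. The downside is that some late doses become recorded omissions, which will add to the interruption count.

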**Table 7-1 Schedule of Study Assessments**

Procedure	Protocol Section	Screening Phase	Treatment Phase										Follow-up Phase				
			Screening a		Rollover Cycle 1			Rollover Cycle 2				End of Treatment	90-day Safety Follow Up	Survival Follow Up			
			Day 1 a	Day 8	Day 15	Day 22	Day 1	Day 8	Day 15	Day 22							
Informed Consent	7.1.1	X															
Demography	7.1.1.2	X															
Inclusion/exclusion criteria	5.2/5.3	X															
Medical history	7.1.1.2	X															
Diagnosis and extent of cancer	7.1.1.2	X															
Prior/concomitant medications	7.1.1.2	X															
Physical examination b	7.3.1	X	X	X	X	X	X	X	X	X	X	X	X	X			
Height	7.3.3	X															
Weight	7.3.3	X	X							X							
Vital signs c	7.3.2	X	X	X	X	X	X	X	X	X	X	X	X	X			
Hematology panel d	7.3.4	X	X	X	X	X	X	X	X	X	X	X	X	X			
Chemistry panel e	7.3.4	X	X	X	X	X	X	X	X	X	X	X	X	X			
Cytokine panel f	7.3.4									In case of a suspected cytokine release syndrome							
Pregnancy test g	7.3.4	X								X							
12-lead electrocardiogram	7.3.4	X															
IMCgp100 administration h	6.1		X	X	X	X	X	X	X	X	X	X	X	X			
Immunogenicity sampling i	7.3.5		X														
Adverse events	8									Continually assessed							
Tumor evaluation per RECISTv.1.1 and modified irRECIST (Refer to Section 6.6.1)	6.6.1	X								Assessed at a minimum of 12 week intervals							
Survival contact	7.2.4																X

**Table 7-1 Schedule of Study Assessments**

Procedure	Protocol Section	Screening Phase	Treatment Phase						Follow-up Phase			
			Rollover Cycle 1		Rollover Cycle 2		End of Treatment	90-day Safety Follow Up	Survival Follow Up			
		Screening a	Day 1 a	Day 8	Day 15	Day 22	Day 1	Day 8	Day 15	Day 22		

irRECIST = immune-related Response Evaluation Criteria in Solid Tumors.
 
a. Screening and Rollover Cycle 1 Day 1 (RC1D1) may be the same day, no procedures or events need to be repeated.
 
b. At Screening (or RC1D1), prior to IMCgp100 infusion, a complete physical examination will be performed. From RC1D8 onwards, a short physical examination will be performed. See Section 7.3.1.
 
c. Frequent vital signs, as per institutional standard, should be implemented during any required inpatient observations at a minimum of every 4 hours. (Refer to Section 7.3.2 for additional details).
 
d. Hematology panel should be obtained at Screening, before every IMCgp100 dose, and at the End of Treatment visit as well.
 
e. Chemistry panel should be obtained at Screening, before every dose of IMCgp100, and at the End of Treatment visit.
 
f. Cytokine panel should be obtained in all patients with a suspected occurrence of cytokine release syndrome. See Section 7.3.4.
 
g. Pregnancy testing is required in all females of childbearing potential. At Screening, a serum pregnancy test must be performed within 72 hours before the first dose of IMCgp100. During the study (Day 1 of each cycle starting with Cycle 2) a serum or urine pregnancy test must be performed. At End of Treatment, a serum or urine pregnancy test must also be performed.
 
h. Please refer to Section 6.1 Study Treatment for details of weekly IMCgp100 administration.
 
i. Immunogenicity samples are to be taken at Day 1 of all odd-numbered cycles and at End of Treatment. All samples are to be collected immediately before IMCgp100 infusion.
 
j. Target and non-target tumors to be assessed for radiographic disease progression by modified irRECIST criteria (refer to Section 7.3.5). Disease assessment to be performed at a minimum of 12 week intervals.
												

### 7.1.1 Screening Assessments

The study IRB/IEC-approved informed consent form (ICF) must be signed and dated before IMCgp100 administration per the rollover study.

Patients will be evaluated against study inclusion and exclusion criteria and safety assessments required at Baseline will be performed. For details of all screening assessments, refer to [Table 7-1](#). Screening assessments must be repeated if performed outside of the specified screening window.

#### 7.1.1.1 Information to be Collected on Screening Failures

The demographic information, informed consent, and screening pages (with reason for screen fail) must also be completed for screen failure patients. No other data will be entered into the clinical database for patients who are screen failures, unless the patient experienced a SAE during Screening, which would be reported in the usual manner via eCRF AE page (See [Section 8.4](#)). If the patient is still enrolled in the parent study at the time of Screening and experiences an SAE, this SAE must be reported to both this rollover study, as well as the initial parent study (see [Section 8.1](#) Assessment of Safety).

A patient who signed the Main Study ICF but failed to be started on study treatment for any reason will be considered a screen failure. If patients are found not eligible after signing the main study consent, the patients will be considered as screening failures, and data will be handled in the same manner.

#### 7.1.1.2 Patient Demographics and Other Baseline Characteristics

Data to be collected will include general patient demographics, relevant medical history and current medical conditions, diagnosis and extent of cancer, prior/concomitant medications, prior procedures, significant non-drug therapies, and any other assessments that are done for the purpose of determining eligibility for inclusion in the study. Prior anti-neoplastic therapies including medications, radiotherapy, and surgery are to be recorded on the separate Prior Anti-neoplastic Therapy eCRF during Screening.

## 7.2 Treatment, Treatment Discontinuation, and Follow-up Phases

### 7.2.1 Treatment Period

A treatment cycle is defined as 4 weeks for the purposes of scheduling procedures and evaluations. Please refer to [Table 7-1](#) for details of the timing of required assessments and visit windows.

### 7.2.2 Discontinuation of Study Treatment

Patients may voluntarily discontinue from the study treatment for any reason at any time. If a patient decides to discontinue from the study treatment, the investigator should make every effort to determine the primary reason for this decision and record this information in the patient's chart and

on the appropriate eCRF pages. Other reasons for discontinuation of study treatment are outlined in [Section 6.6](#).

Patients will be considered withdrawn from treatment if they state an intention to withdraw, fail to return for visits, or become lost to follow-up for any other reason.

The investigator should discontinue study treatment for a given patient if he/she believes that continuation would be detrimental to the patient's well-being.

At the time patients discontinue study treatment, a visit should be scheduled as soon as possible, within 14 days of the last dose of study drug or within 14 days of the decision to permanently discontinue study treatment, at which time all of the assessments listed for the EOT visit will be performed ([Table 7-1](#)). If the decision to withdraw the patient occurs at a regularly scheduled visit, that visit may become the EOT visit rather than having the patient return for an additional visit. An end of treatment eCRF page should be completed, giving the date and reason for stopping the study treatment. End of treatment/premature withdrawal visit is not considered as the end of the study.

Patients who discontinue study treatment should NOT be considered withdrawn from the study. They should return for the assessments indicated in [Section 7](#) and [Table 7-1](#) and be followed for the 90-day Safety Follow-up Period at a minimum. If they fail to return for these assessments for unknown reasons, every effort (eg, telephone, email, postal letter) should be made to contact them. At this time, the reason for study completion should be recorded on the Study Disposition eCRF page.

